## **5. Medications**

Definity will be provided by Lantheus Medical Imaging, Billerica, MA. An FDA Sponsor-Investigator IND will be obtained prior to beginning the trial.

Definity is a sterile, non-pyrogenic suspension of liposome-encapsulated perfluoropropane microbubbles [Goldberg et al 2001; Miller & Nanda 2004]. The contrast agent is composed of a blend of three phospholipids contained in a matrix of sodium chloride, propylene glycol, and glycerin in water. The contrast agent is supplied in a vial that contains the phospholipids and perfluoropropane gas. The microbubble agent is supplied in a standard-size 2 ml vial and is prepared by shaking the vial with the aid of a shaking device (Vialmix: ESPE, Seefeld, Germany). Detailed resuspension instructions are provided in the Definity Product Insert, found in Appendix B.

### **5.1 Administration**

The contrast administration will be an intravenous infusion of 2 vials of Definity/50ml saline through the subjects' vascular port (established as part of their standard of care), with infusion rates of 4 to 10 ml/min (titrated to effect). Next, we will run a power optimization algorithm to establish the individualized acoustic parameter settings for the case (on the first imaging study only). We will use those parameters for all subsequent imaging studies to sweep the area of the LABC to acquire 3D, pulse inversion SHI grayscale volume data. The digital clips and RF data obtained from each 3D SHI injection will be transferred to a PC for off-line analysis. The SHI images will be qualitatively analyzed as described above. This protocol will be followed for all the contrast studies for each subject (except for the power optimization algorithm, which will only be run once for each patient). All subjects will be closely monitored by a physician during and following the study.

## 5.2 Contraindications

Definity should not be administered to patients with known or suspected hypersensitivity to perflutren. The safety of Definity in patients with 1) right-to-left, bi-directional or transient right-to-left cardiac shunts; 2) severe emphysema, pulmonary vasculitis or a history of pulmonary emboli; 3) confirmed or suspected severe liver lesions; and 4) respiratory distress syndrome has not been studied. Therefore, patients with any of these conditions will be excluded from the participation.

## 5.3 Randomization

This is a non-randomized trial; therefore, no randomization procedure is required.

## 5.4 Blinding and Unblinding Methods

This is an open-label trial; therefore, no blinding or unblinding procedures for the trial drug are required.

## 5.5 Storage

Definity vials will be stored in a secure refrigerator, with only the study investigators and research personnel having access. The study research coordinator will be responsible for drug suspension and inventory control.

## **6. Trial Procedures**

### **6.1 Patient Enrollment and Consent**

Subjects eligible for trial enrollment will be identified by the investigators from among TJU patient population who are who are undergoing neoadjuvant chemotherapy. An investigator or research coordinator will explain the study to the patient. The patient will be given time to consider the risks and benefits of the study and ask questions about participation. The consent form will be reviewed with the patient and then the patient will be given the form to review. If consent interview is conducted by a coordinator, a study investigator will then discuss the study with the subject and answer any additional questions. The patient, person conducting study interview (if applicable), and a study investigator will all sign the consent form. The patient will be given a copy of the signed consent form for her records.

### **6.2 Screening Assessments**

Screening assessments will be performed within 24 hours prior to the administration of Definity. Trial participants will have the presence of inclusion criteria and absence of exclusion criteria verified by providing a medical history. A full demographic profile, known drug allergies or intolerances, and a review of the subject's medical/surgical history will be recorded. If the subject is a woman of childbearing potential, she will have a urine pregnancy test (the results of which will be made available to the subject prior to study initiation).

### **6.3 Ultrasound Imaging**

The US examinations will be performed by a qualified sonographer. Procedures and equipment for this trial will be used in accordance with typical clinical procedures. All trial procedures will be conducted in accordance with Good Clinical Practice. For the ultrasound examination, the patient will be asked to lie in the supine position. Acoustic coupling gel will be applied to the breast area of interest. A baseline US grayscale scan will be used to identify the breast cancer seen by mammography (or another concomitant imaging mode such as US or MRI). Standard PDI of the tumor will also be performed. If the mass is too large to be completely imaged by the 4D10 L probe, the most vascular region seen on 2D PDI will be selected for the 3D SHI studies.

To perform the 3D SHI imaging, US software has been modified by GE Medical Systems on the clinical system, the Logiq 9 scanner, to permit acquisition of subharmonic data. All acoustic parameters have been verified and are all within the current standards of the machine, making the modified ultrasound system a non-significant risk device. US imaging will be performed at a transmit frequency of 5.8 MHz and the subharmonic obtained at 2.9 MHz. Using this setup, acoustic pressure amplitudes will all be below 1.5 MPa peak negative pressure, 2.5 MPa peak positive pressure ( $MI < 0.33$ ).

The contrast administration will be an intravenous infusion of 2 vials of Definity/50ml saline through the subjects' vascular port (established as part of their standard of care), with infusion rates of 4 to 10 ml/min (titrated to effect). Next, we will run a power optimization algorithm to establish the individualized acoustic parameter settings for the case (on the first imaging study only). We will use those parameters for all subsequent imaging studies to sweep the area of the LABC to acquire 3D, pulse inversion SHI grayscale volume data. The digital clips and radio frequency data obtained from each 3D SHI injection will be transferred to a PC for off-line analysis. The SHI images will be qualitatively analyzed as described above. This protocol will be followed for all the contrast studies for each subject (except for the power optimization algorithm, which will only be run once for each patient). All subjects will be closely monitored by a physician during and following the study.

## 6.4 Safety Monitoring

Patients will be monitored for AEs during and immediately after contrast administration. All other procedures will be performed according to TJU standard of care.

## 6.5 Safety Assessments

Adverse events will be monitored during the entire procedure. Specifically, the patient will be monitored with non-leading questions to monitor the patient for the transient side effects that are described below.

### 6.6.1 Risks/Benefits Assessment.

Serious cardiopulmonary and allergic reactions including fatalities have occurred during or following administration of Definity, causing the FDA to place a black box warning on the agent. However these occurrences have been rare (less than 1 in 5,000 patients). As a result, patients with cardiac shunts or unstable cardiopulmonary conditions will be excluded. The majority of adverse events from Definity were mild to moderate in severity. Transient side effects that have been described as possibly related to Definity administration include headache (2.3%), back and renal pain (2.1%), flushing (1.1%) and nausea (1.0%). Hypersensitivity reactions to perflutren may occur, although rare.

Clinically significant adverse effects from the administration of Definity are unlikely based on our previous experiences. The use of contrast with the new US imaging techniques is expected to provide significantly more information than from conventional US techniques. This may lead to additional information about the characteristics of breast tumors which may be clinically relevant.

To minimize and/or eliminate risks a nurse will be present during the entire procedure. Adverse events will be monitored during the entire procedure.

### 6.6.2 Adverse Events

An AE includes any condition that was not present prior to trial treatment, but appeared following initiation of trial medication; any condition that was present prior to trial treatment, but worsened during trial medication; or any condition, of which the subject has a history, that was not present prior to trial medication initiation but reappeared following administration of Definity. This would include conditions that are likely to be associated with an underlying or intermittent disease (e.g., angina, flu, etc.).

The subjects will be monitored for AEs during the entire procedure. All AEs, including observed or volunteered problems, complaints, signs or symptoms, and diagnoses, occurring from the initiation of Definity dosing until the completion of the Definity administration will be recorded on a serious or non-serious AE data form, whether or not associated with the use of the trial medication. All adverse events are reported to the Clinical Trial Support Office (CTSO) via the password protected Kimmel Cancer Center Adverse Event Reporting System. In addition all unexpected and serious adverse events (SAEs) are reported to the TJU IRB and to the Food and Drug Administration (FDA) if applicable. The investigator is required to submit all unexpected and serious adverse events to the TJU IRB and the DSMB within 48 hours. Fatal adverse events related to treatment which are unexpected must be reported within 24 hours to the TJU IRB and the DSMB through CTSO. Fatalities not related to the study drug/device must be reported within 5 days.

The AE forms will include: subject identification number and initials; subject's date of birth, gender, and ethnicity; date of Definity administration; signs/symptoms and severity; date of onset; date of resolution or death; relationship to the study drug; action taken; concomitant medication(s) including dose, and route and duration of treatment.

Whenever possible, the AE will be evaluated and reported as a diagnosis rather than individual signs and symptoms. If a definitive diagnosis is not possible, the individual signs and symptoms will be

recorded. The investigator will evaluate and note the duration, intensity, and relationship to (association with) the Definity administration, the action taken, and the determination of seriousness for each AE.

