#### Definity Clinical Safety

Definity is well tolerated and has been used extensively in echocardiography applications [Goldberg et al 2001]. In pre-market clinical trials, Definity was administered to 1716 patients. In these patients 269 (8.4%) reported at least one adverse event. Of these events, 26 were classified as serious including 19 (1.1%) patients experiencing serious cardiopulmonary symptoms including eight deaths. The deaths occurred several days after activated Definity administration and appear to be related to the course of underlying disease. Of the 11 other serious adverse events, which appeared within days of the drug administration (2-15 days), all appeared to be a progression of underlying cardiac and non-cardiac disease. However, a role for Definity in the initiation or course of these adverse events cannot be ruled out.

Of the reported adverse reactions following the use of Definity the most frequently reported were headache (2.3%), back and renal pain (2.1%), flushing (1.1%), and nausea (1.0%). Additional risks

associated with the contrast material are described in the attached Definity Product insert (Appendix B).

All of the non-serious reported side-effects have been transient, usually lasting only a few minutes.

Table 1.

Selected Adverse Events Reported in  $\geq 0.5\%$  of the Subjects who Received Definity in Controlled Clinical Studies

No. of Patients Exposed to Definity	1716	
No. of Patients Reporting an Adverse Event	269	(8.8%)
Central and peripheral nervous system	54	(3.2%)
Headache	40	(2.3%)
Dizziness	11	(0.6%)
Body as a Whole	41	(2.4%)
Back/Renal Pain	20	(1.2%)
Chest Pain	13	(0.8%)
Digestive System	31	(1.8%)
Nausea	17	(1.0%)
Vascular (extracardiac) disorders	19	(1.1%)
Flushing	19	(1.1%)
Application Site Disorders	11	(0.6%)
Injection Site Reactions	11	(0.6%)

Additional information concerning pre-clinical and clinical experience with Definity, including the dosing levels and reported subject complaints, can be found in the Definity Package Insert that is included as Appendix B.

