## SERIOUS ADVERSE EVENTS

A "serious" AE (SAE) is defined as a significant clinical hazard, contraindication, or precaution that:

Results in death

- Is life-threatening (In the opinion of the investigator, there is an immediate risk of death from the AE as it occurred. This does not include an AE that had it occurred in a more serious form may have caused death.)
- Results in a persistent or significant temporary disability/incapacity defined as a substantial disruption of a person's ability to conduct normal life functions
- Results in or prolongs an existing in-patient hospitalization (an overnight stay in the hospital, regardless of length) [Note: A hospitalization for an elective procedure or treatment which is not associated with an AE, hospitalization for a pre-existing condition which did not worsen, and hospitalization for reasons of convenience or observation, do not constitute an SAE.]
- Is a congenital anomaly/birth defect (in offspring of a subject taking the trial medication, regardless of time to diagnosis)
- Is an important medical event that may not result in death, be life-threatening, or require hospitalization but based upon the appropriate medical judgment, the event may jeopardize the subject and may require medical or surgical intervention to prevent one of the outcomes listed for the definition of a serious adverse experience.

All unexpected and serious adverse events are reported to the TJU IRB and to FDA if applicable.

The investigator is required to submit all unexpected and serious adverse events to the TJU IRB and the

data safety monitoring board within 48 hours. Fatal adverse events related to treatment which are unexpected must be reported within 24 hours to the TJU IRB and the DSMB through CTSO.

The written report for any SAEs that occur during the study, whether or not related to the Definity administration will be submitted immediately (within 24 hours) to the TJU Institutional Review Board.

The designated medical monitor will review all serious and unexpected adverse events associated with the protocol and provide an unbiased written report of the event within 10 calendar days of the initial report. At a minimum, the medical monitor will comment on the outcomes of the adverse event and relationship of the event to the Definity administration.

A copy of the SAE will be retained on file with the respective subject's data forms.

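### Section 6.6.2 stops adverse event recording when the infusion ends, which conflicts with the observation and SAE reporting that the protocol requires elsewhere

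*Combined protocol and SAP*

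**What the plan says.** The only explicit recording window is in section 6.6.2. AEs "occurring from the initiation of Definity dosing until the completion of the Definity administration will be recorded", on the form for serious or for non-serious events, irrespective of causality. One rule therefore covers both forms, and it closes when the agent has been given.

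Other parts of the document reach further:

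- The AE definition that opens section 6.6.2 covers conditions that appear, worsen or recur after the agent is started. It has no end point.
- Section 6.4: "Patients will be monitored for AEs during and immediately after contrast administration".
- Section 4 (both the contrast agent text and the US Examination Protocol), section 5.1 and section 6.3 have a physician watch each subject during the study and afterwards. No length is given for the observation afterwards.
- Section 6.6.1: "Serious cardiopulmonary and allergic reactions including fatalities have occurred during or following administration of Definity".
- The Serious Adverse Events section asks for a written report of every SAE arising *during the study*, related or not, which "will be submitted immediately (within 24 hours) to the TJU Institutional Review Board".

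Reporting deadlines appear in two places. Section 6.6.2 gives 48 hours for unexpected and serious events, 24 hours for unexpected treatment-related deaths, and 5 days for unrelated deaths. The Serious Adverse Events section repeats the first two and adds the 24-hour report for any SAE.

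**The concern.** The recording rule is narrower than the period in which the protocol has staff watching the subject. A headache, flush or allergic reaction that begins shortly after the infusion stops would be seen by the observing physician, yet as written it does not go on an AE form. The protocol itself says that serious reactions can follow administration as well as accompany it.

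Each subject has four contrast studies during chemotherapy, in what section 4 calls an off-label use. With 20 to 50 subjects, a few unrecorded reactions could visibly change the reported rates. The forms also feed the Clinical Trial Support Office, the IRB and the data safety monitoring board, so a gap at the recording step can carry through to oversight.

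The SAE deadlines add a second problem: for some events the site has two different deadlines for the same recipient.

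**Working it through.** **1. Length of the recording window.** The protocol states no duration, so there is no figure to reproduce. Inputs from section 5.1: "intravenous infusion of 2 vials of Definity/50ml saline", "with infusion rates of 4 to 10 ml/min (titrated to effect". Section 5 gives a vial size of 2 ml. Duration = volume / rate.

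- 50 ml: 50/10 = 5.0 min; 50/4 = 12.5 min.
- 54 ml, assuming two full vials add to the saline (50 + 2 × 2): 54/10 = 5.4 min; 54/4 = 13.5 min.

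The range is 5 to 13.5 minutes per contrast study, or 4 × 5 = 20 to 4 × 13.5 = 54 minutes per subject over four studies. This assumes that the whole volume is infused without a pause. The rate is titrated, so actual times may differ.

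**2. The sections side by side.**

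| Place | Period covered | Applies to |
|---|---|---|
| 6.6.2, recording rule | Start to completion of Definity | Serious and non-serious AEs |
| 6.6.2, AE definition | From start of the agent, no end | All AEs |
| 6.4 | During and just after contrast | Monitoring of AEs |
| 4, 5.1, 6.3 | Imaging study and an unspecified time after | Physician observation |
| Serious Adverse Events | *During the study*, undefined | SAE reporting |

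For non-serious AEs, nothing extends recording past the first row. For SAEs, the last row contradicts the first. Nothing describes asking about, or searching for, events between one contrast study and the next.

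**3. Timing of the pre-market serious events (Definity Clinical Safety).** The protocol reports 26 serious events, including 19 patients with serious cardiopulmonary symptoms, 8 of whom died. The stated percentage reproduces: 19/1716 = 1.1%. The deaths are placed several days after dosing. The 11 others are those "which appeared within days of the drug administration (2-15 days". 8 + 11 = 19, and 26 − 19 = 7 have no stated onset. Putting 19 over 26 treats patients and events as one count, which is an assumption. All 19 would fall outside a window of 5 to 13.5 minutes.

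**4. Reporting clocks to the IRB.**

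| Event | Section 6.6.2 | Any-SAE rule | Conflict |
|---|---|---|---|
| Unexpected, related death | 24 h | 24 h | No |
| Unexpected, serious, non-fatal | 48 h | 24 h | Yes |
| Unrelated death | 5 days (5 × 24 = 120 h) | 24 h | Yes |

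**The case against.** The strongest reply is that serious events are not in fact cut off at the end of the infusion. The Serious Adverse Events section wants a report of every SAE in the study, and section 6.7.1 ties completion to four contrast studies over the cancer treatment. The form fields for onset and for resolution or death, and the 5-day clock for unrelated deaths, also presuppose later events. This stands: for SAEs the fault is a contradiction, not a plain stop. It does not settle the matter, because the study period is undefined and no method of finding interval events is given.

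Second, all 19 late pre-market events were serious, so they belong to the category with the wider reporting text. The protocol describes non-serious side effects as transient, usually lasting minutes. The first half is right. The second concerns how long a reaction lasts, not when it starts; a brief reaction that begins after the infusion is still unrecorded.

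Third, the background section attributes the late events to progression of underlying disease, and section 6.6.1 calls serious reactions rare, at fewer than 1 in 5,000 patients. Both statements belong beside the count of 19. But section 6.6.2 records AEs irrespective of causality, and causality is assessed afterwards, so attribution is no reason to leave events unrecorded.

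Fourth, a reader might infer that all three reporting clocks conflict. They are mostly tiers by type of event; only the two pairings marked above collide.

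Finally, safety is neither an objective nor a planned analysis, and collecting every AE between scans would bring in much chemotherapy toxicity. That is a fair reason to limit collection between scans to SAEs. It does not excuse leaving observed reactions unrecorded.

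**Conclusion.** The point holds as an internal inconsistency with a practical consequence. Followed literally, section 6.6.2 records 5 to 13.5 minutes per contrast study, if the full 50 to 54 ml is infused without interruption. Non-serious reactions seen in the observation afterwards are left out, with no other text to catch them. SAEs are subject to two incompatible rules, and two types of SAE carry conflicting IRB deadlines. The safety record could be under-reported. The documents do not allow an estimate of how many events would be missed.

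A reader might go further and infer that delayed serious events would never be recorded, that the data safety monitoring board would not see them, or that the 19 late pre-market events show delayed harm from Definity. The documents do not support these readings. SAE reporting across the study is required, unexpected and serious events go to the board, and a medical monitor reviews them within 10 calendar days. Onset is given for 19 of the 26 events only. The protocol attributes those 19 to underlying disease, while saying that a role for Definity cannot be excluded.

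**What to change.** Amend section 6.6.2 in three respects.

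- Record all AEs, serious and non-serious, from the start of the infusion to the end of the post-scan observation that the protocol already requires. State in the text when that observation ends, so that sections 6.3, 6.4 and 6.6.2 agree.
- Record SAEs throughout study participation, in line with the Serious Adverse Events section, and define the period meant. Ask about SAEs since the previous scan at each contrast study already scheduled. That means the second, third and fourth studies: 3 × 20 = 60 to 3 × 50 = 150 questions over the trial. These questions cannot reach events after the fourth study, so the definition should say whether participation ends there.
- Reconcile the 24-hour IRB report for any SAE with the 48-hour and 5-day clocks, preferably in one table by event type and recipient. Which deadline governs is for the sponsor and the IRB to settle.

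The cost is a wording amendment and an added form question at three visits that take place anyway. The small downside is that some SAEs due to chemotherapy will be recorded as background; the existing causality assessment can classify them.
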